9.7 Study Withdrawal

All subjects have the right to withdraw at any point during the treatment without prejudice. The investigator can discontinue any subject at any time if medically necessary. If a subject withdraws prematurely from the study, a genuine effort must be made to determine the reason(s) why the subject discontinued the study. The reason must be recorded.

9.8 Subjects Compensation

Subjects will be compensated up to 100 USD for traveling and parking fee, against receipts. Half of the payment and up to 50 USD will be given at 12 months visit, and 50 USD at 24 months visit. The payment will be given by the study staff (e.g. site study coordinator/ clinical administrator/ investigator).

10.0 Data Handling

10.1 Subject Identification

The subjects will be identified by a 2 digit sequential subject number. The initials for each subject will also be included on CRFs. In this way, information contained in the study records will be kept as confidential as possible. The allocation subject number will be as follows: XVT __ __ (Site number) - __ __ __ (subject enrollment number). Subject initials will include three letters, first letter of first name, middle name and last name. In cases where subject does not have a middle name a dash sign will be entered.

10.2 Confidentiality

All medical records associated with this clinical investigation will be made available for review by designated personnel and governmental agencies involved. The results of the study may be published in the future for scientific purposes, but the identity (name) of each subject will not be revealed. All records will be stored in a secure area at the investigator's facility

10.3 Case Report Forms

The data from this study will be collected using the following forms:

CRF 1 – Initial Data Sheet

CRF 2 – Operative Form

CRF 3 – Follow-Up Form (to be used for all follow-up visits)

CRF 4 – Adverse Event Form

CRF 5 – Protocol Deviation Form

10.4 Administrative Forms

The administrative forms include the Subject Log Form.

10.5 Record Retention

The investigator will retain any and all clinical trial material (documentation, photographs, etc.) for a period of six (6) years following the completion of the study.

11.0 Safety

At each visit, the ocular health of each subject will be assessed. The cornea, anterior chamber, trabecular meshwork, and implant location (if applicable) will be examined. If any abnormalities are observed, they are to be noted (type and location) within the case report forms.

11.1 Adverse Events

Any ocular adverse events occurring during the trial whether they are considered to be device related or not must be documented in the subject's records. Date and time of the event, its severity, treatment (if any) and the assessed relationship of the event to the study will be recorded on CRF 4 Adverse Event Form. Conditions which exist at the time the subject is enrolled do not need to be recorded on the Adverse Event Form as adverse events unless they increase in severity during the study.

A brief overview of the differences between anticipated, unanticipated and serious adverse events is provided below:

- **Anticipated Adverse Events**

Anticipated adverse events include those that might reasonably be expected to occur in this study because they are associated with glaucoma surgical procedures.

- **Unanticipated Adverse Events**

Unanticipated adverse device effects (UADE) include any serious adverse effects on health or safety or any life-threatening problem or death caused by or likely directly related to the Ex-PRESS mini shunt or the placement of the Ex-PRESS mini shunt within the eye that are not typically associated with glaucoma surgical procedures.

- **Serious Adverse Events**

Serious adverse events include those events that require or prolong hospitalization, require surgical intervention, are sight or life-threatening or fatal, or result in significant disability or incapacity.

11.2 Reporting Adverse Events

All serious adverse events (whether anticipated or unanticipated) must be reported to the reviewing IRB according to their guidelines given..

All adverse events should be documented by completing CRF 4, Adverse Event Form and a specific IRB AE form (if applicable).

Identification and collection of adverse event information will be the responsibility of the study investigator. The investigator will follow the Declaration of Helsinki in order to ensure the safety of all subjects.

11.3 Type and duration of follow-up after adverse events

The investigator is responsible for recommending the type and duration of follow-up for each subject who experiences an adverse event. All events must be followed until study completion, complete resolution or resolution with sequelae. All details must be documented on CRF 6, Adverse Event Form.

12.0 Statistical Analysis

The data provided from this randomized controlled study are intended to provide a reasonable assurance of safety and effectiveness for the Ex-PRESS mini shunt compared to standard trabeculectomy.

The primary safety and effectiveness end points are provided in sections 7.1-7.4 of this protocol. The data will be analyzed using the Fishers exact test p-value and Student's paired *t* test p-value comparison. Success rate will be analyzed using Kaplan-Meier survival analysis curves. [Phakic and pseudophakic patients will be explored as a possible covariate in the efficacy and safety analysis.](#)

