2.0 Study Purpose

The purpose of this study is to compare the safety and effectiveness of the Ex-PRESS mini glaucoma shunt to trabeculectomy in reducing the number of post operative complications, reducing intraocular pressure (IOP) and reducing the use of hypotensive medications in subjects with open-angle glaucoma or ocular hypertension.

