7.1 Primary Effectiveness End Points

The primary effectiveness measure will be qualified and complete success rate defined as $IOP \leq 18 \text{ mmHg}$ with or without medications in the test group as compared to complete and qualified success rate in the concurrent control group at 12 months.

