7.2 Secondary Effectiveness End points

The secondary effectiveness measure will be qualified and complete success rate defined as $IOP \leq 18 \text{ mmHg}$ with or without medications in the test group as compared to qualified and complete success rate in the concurrent control group at 24 months.

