9.0 Study Protocol

9.1 Study Synopsis

Title:	A prospective randomized multi-center study to compare the Ex-PRESS™ to trabeculectomy in patients with open angle glaucoma who failed medical treatment and for which filtering surgery is indicated
Protocol Number:	XVT-01
Number of Sites:	7 sites were approved.
Study Period:	2 year, 10 visits: Pre-operation, day of surgery, day 1, 1-2 Weeks, Months 1, 3, 6, 12, 18 and 24 post operation. Additional visits will be performed and recorded as required for the optimal treatment and follow up of the patient. Additional visits are defined as visits that were not preplanned and considered emergent.
Study design:	A prospective, two arm, active control, unmasked, randomized study
Objectives:	A prospective randomized trial to compare the safety and efficacy of the Ex-PRESS to trabeculectomy in patients with open angle glaucoma who failed medical or are allergic to medical treatment and for which filtering surgery is indicated
Control Arm	Subjects undergoing trabeculectomy with the use of Mitomycin C
Treatment Arm	Subjects undergoing Ex-PRESS Under Scleral Flap implantation procedure with the use of Mitomycin C
Subject Population:	Open angle glaucoma patient's candidates for filtering surgery. The patients may have a history of cataract phacoemulsification surgery.
Sample Size:	Total of 120 subjects with 60 subjects in each arm. Each site can enroll a maximum of 30 subjects and a minimum of 5 subjects for each study arm.
Follow-up duration:	2 years
Target enrollment period:	Up to 1 year

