9.4.2 Baseline Evaluation

After obtaining an understanding of the purpose of this study, reviewing and signing the informed consent form, all potential subjects will undergo an examination in order to determine their eligibility for this study.

The screening examination will consist of applanation tonometry to measure IOP, general slit-lamp biomicroscopy to review the overall health of the eye, visual acuity (VA) measurements, and a review of current medications and prior surgeries. All information should be compared to the specific inclusion and exclusion criteria in order to determine if the subject is eligible to participate in the study.

The following criteria are provided below to assist with appropriate screening for all subjects in this study:

- **Diagnosis**

Investigator is to provide the diagnosis in each eye, as either ocular hypertension (elevated IOP without evidence of visual field loss or cupping of the optic nerve head) or glaucoma (elevated IOP with either glaucomatous visual field loss, as judged by automated threshold visual field testing, or cupping of the optic nerve head).

- **Measurement of intraocular pressure**

Each time IOP is measured, the surgeon or technician is to utilize a Goldmann tonometer, however, an independent observer should read the measurement and then record the measurement to minimize observer bias.

Two measurements should be taken and the mean recorded on the case report form UNLESS they differ by more than 2 mmHg in which case a third measurement is taken and the median value is recorded.

- **Visual Field Examination**

Visual fields must be automated threshold visual fields (e.g., 30-2 or 24-2 Humphrey). SITA Standard visual fields are required. Visual fields must be reliable, defined as less than 33% false positives, false negatives, and fixation losses.

The visual field must be performed within three to six months of study entry and meet the aforementioned requirements. Both the test eye and the fellow eye should have visual field data.

Visual fields are to be performed with a non-dilated pupil unless, in the opinion of the investigator, the pupil is so miotic that dilation is required (e.g., < 3 mm). If dilation was performed at baseline, it should be performed at all subsequent visual field examinations. However, dilation should not be performed before the IOP measurement on the appropriate visits.

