For OAG subjects and in accordance with the American Academy of Ophthalmology (AAO) Preferred Practice Patterns, the severity of glaucoma damage can be assessed as follows: (1) Mild – characteristic optic nerve abnormalities are consistent with glaucoma, but there is a normal visual field and (2) Moderate – visual field abnormalities are in one hemifield and not within 5 degrees of fixation.

For OHT subjects, qualifying visual fields must be normal and reliable in the study eye.

- Cup-to-Disc Ratio

A numerical expression indicating the percentage of disc occupied by the optic cup. A score from 0.1 to 0.9 (in 0.1 increments) should be indicated.

- Visual Acuity

Best corrected visual acuity will be measured at baseline and at each follow-up visit. Visual acuity will be measured using Snellen line method.

If a subject satisfies all inclusion and exclusion criteria the subject will be enrolled into the study. The subject is then randomized to participate in either Group A or Group B using the sealed envelope method of randomization.

Group A

Subjects will undergo implantation of the Ex-PRESS mini glaucoma shunt.

Group B

Subjects will undergo standard trabeculectomy.

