9.6 Follow up

All subjects will participate in defined follow-up visits for two years. Follow up visits include day of surgery, day 1, 1-2 Weeks, Months 1, 3, 6, 12, 18 and 24 post surgery. Additional visits will be performed and recorded as required for the optimal treatment and follow up of the patient. Additional visits are defined as visits that were not preplanned and considered emergent. Table 1 presents the activities to be performed at each follow up visit.

Table 1: Follow-up Activities

Activity	Screening	Surgery	1 Day	1-2 Wk	1 Mo	3 Mo	6 Mo	12 Mo	18 Mo	24 Mo
Ophthalmology Exam	X									
Medical History	X									
Medication Assessment	X		X	X	X	X	X	X	X	X
Visual Field	X							X		X
CD ratio	X							X		X
Slit-lamp Exam	X		X	X	X	X	X	X	X	X
Visual Acuity	X		X	X	X	X	X	X	X	X
Fundus Exam	X							X		X
IOP	X		X	X	X	X	X	X	X	X
Procedure		X								
Adverse Event Assessment		X	X	X	X	X	X	X	X	X
Protocol Deviation Assessment		X	X	X	X	X	X	X	X	X

- Intraocular pressure measurements during follow-up visits

Each time IOP is measured, the surgeon or technician is to utilize a Goldmann tonometer, however, an independent observer should read the measurement and then record the measurement to minimize observer bias.

Two measurements should be taken and the mean recorded on the case report form UNLESS they differ by more than 2 mmHg in which case a third measurement is taken and the median value is recorded.

All attempts should be made to conduct each follow-up evaluation within the specified time intervals (Table 2).

Table 2: Follow up examination schedule

Follow up visit	Acceptable Time Interval (Days from Procedure)
Day 1 pos-op	Day 1 post op
7-14 days post-op	7-14 days post-op
1 month post-op	30 days \pm 7 days
3 months post-op	90 days \pm 14 days
6 months post-op	180 days \pm 21 days
12 months post-op	360 days \pm 30 days
18 months post-op	540 days \pm 30 days
24 months post-op	720 days \pm 30 days

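### The only named test suited to continuous data is a paired t test, so the plan has no valid between-arm test for IOP as a quantity or for medication use

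*Combined protocol and SAP*

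**What the plan says.** Section 12.0 is the whole analysis plan. On tests it says: "The data will be analyzed using the Fishers exact test p-value and Student's paired *t* test p-value comparison". It adds Kaplan-Meier curves for the success rate and lens status as a possible covariate. It does not say which test goes with which outcome, and it names no unpaired t test, ANCOVA, mixed model or rank test.

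The synopsis (section 9.1) gives the design as "A prospective, two arm, active control, unmasked, randomized study". Section 9.4.2 gives the allocation: "The subject is then randomized to participate in either Group A or Group B". Nothing describes matched subjects or a fellow-eye control.

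Section 2.0 sets the purpose as a comparison of the shunt with trabeculectomy in "reducing the number of post operative complications, reducing intraocular pressure (IOP) and reducing the use of hypotensive medications". Sections 7.1 and 7.2 define effectiveness as the proportion with IOP of 18 mmHg or less at 12 and 24 months, "with or without medications in the test group as compared to complete and qualified success rate" (section 7.1; section 7.2 is nearly identical). Sections 7.3 and 7.4 define safety by the occurrence or incidence of events. After defining an IOP spike, section 7.4 adds that every measurement, not only the spikes, will be gathered and analyzed.

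**The concern.** A paired t test needs a natural pair. Here the only natural pair is a subject's own baseline and follow-up value, and that comparison shows whether IOP fell within one arm. It does not show whether IOP fell further in one arm than in the other, which is what section 2.0 asks.

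The success endpoint fills the gap only in part. It reflects IOP through one cut-off. It counts success regardless of medication, so a subject on no drug and a subject on several count the same, and it cannot compare medication use. The early postoperative IOP values covered by section 7.4 have no between-arm method beyond the spike incidence.

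Two things are at stake. If results report only paired p-values for IOP and medications, two very small p-values side by side may be read as evidence about the difference between arms. If a between-arm method is instead chosen later, it will be chosen in an unmasked trial after data have been seen.

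**Working it through.** **No figure of the plan is in dispute.** The documents give 60 subjects per arm (sections 1.0, 9.1 and 9.3.1) without an effect size, SD, alpha or power, so there is no calculation to reproduce. The sample size is the only input below that comes from the documents. The IOP falls, SDs and loss to follow-up are assumptions.

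**Step 1. What the paired test could mean.** Three readings are open.

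- Baseline against follow-up within each arm: valid, but not a comparison of arms.
- Subjects paired across arms: no pairing exists. An arbitrary one needs equal numbers analyzed in each arm and leaves 59 degrees of freedom instead of 118. In a simulation of 20,000 trials (60 per arm, SD of change 4 to 6 mmHg) it kept a type I error of about 5%, and its power for a 3 mmHg difference was 77% to 98%, about that of the unpaired test. The objection is that the result depends on an arbitrary ordering of subjects, not that the error rate fails.
- A slip for the unpaired test: possible, but the text does not say so.

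**Step 2. Formulas.**

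- Within an arm: t = fall / (SD/√n), on n − 1 degrees of freedom.
- Between arms: t = difference / (SD × √(2/n)), on 2n − 2 degrees of freedom.

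**Step 3. Numbers at n = 60 and SD of change 6 mmHg.**

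Within-arm standard error: 6/√60 = 0.775. Between-arm standard error: 6 × √(2/60) = 1.095. Critical t on 118 degrees of freedom: 1.980, so the CI half-width is 2.17.

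| Mean falls (mmHg) | Within-arm t | Within-arm p | Between-arm difference (95% CI) | Between-arm p |
|---|---|---|---|---|
| 8 v 8 | 10.33, 10.33 | 7.6e-15 in both | 0 (−2.17 to 2.17) | 1.0 |
| 10 v 8 | 12.91, 10.33 | 7.8e-19, 7.6e-15 | 2.0 (−0.17 to 4.17) | 0.070 |
| 10 v 7 | 12.91, 9.04 | 7.8e-19, 9.9e-13 | 3.0 (0.83 to 5.17) | 0.007 |

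The within-arm columns look alike in all three rows. The between-arm columns run from no difference to a clear one.

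**Step 4. Sensitivity to the assumed SD and to loss.**

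| Analyzed per arm | SD of change | Between-arm p, 10 v 8 | Between-arm p, 10 v 7 | Largest within-arm p |
|---|---|---|---|---|
| 60 | 4.5 to 8 | 0.016 to 0.17 | 0.0004 to 0.042 | 6.4e-9 |
| 48 (20% loss) | 4.5 to 8 | 0.032 to 0.22 | 0.0015 to 0.069 | 2.2e-7 |

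Throughout this range the within-arm p-values are negligible whether or not the arms differ, so they cannot inform the comparison.

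**The case against.** The strongest reply is that this is an omission, not a misuse. Section 12.0 never says that the paired test will compare the arms. Within-arm change is a legitimate use, and a misreading of the results would arise only if paired p-values were reported alone. Mean IOP and number of medications are not among the endpoints of section 7; they enter through the purpose statement, which speaks of medication use and not of a count. ANCOVA and a rank-sum test are also more than the minimum needed.

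Most of this stands, and it limits the weight of the point. It does not close the gap. On the most favorable reading, a stated comparison still has no between-arm test, and section 7.4 still promises an analysis of IOP values for which no between-arm method is given.

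A reader might infer three stronger things that the documents do not support.

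- That the primary analysis is invalid. The section 7 endpoints are rates or incidences, and Fisher's exact test is applicable to them as a test of difference.
- That those endpoints are therefore fully served. Section 8.0 claims efficacy on a par with trabeculectomy; whether a test of difference can support such a claim is a separate point.
- That the information lost by reducing IOP to success or failure at 18 mmHg counts against the paired test. That loss follows from the choice of endpoint, not from the test named here.

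**Conclusion.** The point holds as a gap of minor to moderate weight. The plan names no valid between-arm test for IOP as a quantity, for medication use, or for the postoperative IOP measurements of section 7.4. The primary endpoint does not depend on it.

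This conclusion rests on the text alone: the list of tests in section 12.0, the parallel unmatched design, and the purpose in section 2.0. That the paired test is meant for continuous data is an inference, because no test is tied to an outcome. The calculation only illustrates why paired p-values cannot stand in for a comparison of arms. It is not an estimate of what this trial will find.

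**What to change.** In section 12.0, replace the paired t test wording with:

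> As supportive analyses, not adjusted for multiplicity, IOP at months 12 and 24 will be compared between arms by ANCOVA with treatment and baseline IOP as terms (adjusted mean difference with 95% CI), and the number of medications at months 12 and 24 by the Wilcoxon rank-sum test. IOP at the early postoperative visits will be compared between arms by the same ANCOVA and reported descriptively with 95% CIs. Paired t tests will be used only to describe change from baseline within each arm.

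An unpaired two-sample t test for IOP is the minimum correction.

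The cost is a few sentences and no new visit or assessment. Table 1 in section 9.6 already schedules IOP and a medication assessment at screening and at every follow-up visit from day 1 to month 24, and section 9.4.2 includes "a review of current medications and prior surgeries" at screening. The documents do not say that a count of medications is recorded, so it would have to be derived from those assessments.

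The downside is a few more unadjusted tests. For the four at months 12 and 24, the chance of at least one p below 0.05 when there is no difference is 1 − 0.95^4 = 18.5% if they were independent, hence the supportive label. The wording does not settle how IOP after further glaucoma surgery is handled, which needs its own rule.

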9.3 Study Population

9.3.1 Number of Subjects

A total of 120 subjects will be enrolled into the study with 60 subjects in each arm.

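### Section 12.0 names lens status as a possible covariate but gives no method that adjusts the arm comparison for it, and its only test for continuous data, a paired t test, does not compare the two arms

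*Combined protocol and SAP*

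**What the plan says.** Section 12.0 is the whole analysis plan. On tests it says: "The data will be analyzed using the Fishers exact test p-value and Student's paired" t test comparison. On success it says: "Success rate will be analyzed using Kaplan-Meier survival analysis curves". On covariates it says only: "Phakic and pseudophakic patients will be explored as a possible covariate in the efficacy and safety analysis". It names no regression model, no stratified test and no rule for when lens status enters. It does not say what is paired in the t test, and it does not mention baseline IOP.

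The rest of the protocol supplies the context:

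- Size: "A total of 120 subjects will be enrolled into the study with 60 subjects in each arm" (section 9.3.1).
- Primary effectiveness endpoint: binary, success at 12 months on an IOP threshold of 18 mmHg (section 7.1). Section 7.2 repeats it at 24 months.
- IOP as a quantity: lowering it is part of the study purpose (section 2.0). Section 7.4, on pressure spikes, adds that all measurements will be analyzed.
- Baseline data: IOP and prior surgeries are recorded at screening (section 9.4.2 and Table 1), and entry requires IOP above 18 mmHg (section 9.3.3). Earlier phacoemulsification is allowed (sections 9.1 and 9.3.2), so both lens groups can be expected.
- Randomization: sealed envelopes, with no stratification factor stated (section 9.4.2).

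**The concern.** There are two linked gaps.

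1. The plan names a covariate but gives no way to use it in the comparison of arms. Fisher's exact test and the t test take no covariate. Kaplan-Meier curves can be drawn by lens group, but that describes subgroups and gives no adjusted arm effect.

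2. The only test named for continuous data is paired. The two arms contain different subjects, so there is no pairing between them. If the pairs are baseline and follow-up values of the same subject, the test asks whether IOP fell within an arm. With entry restricted to IOP above 18 mmHg, some fall is expected from regression to the mean alone, and a significant fall in each arm says nothing about which arm did better.

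At stake is the between-arm IOP comparison, for which the plan has no suitable method, and some precision on it. Randomization is not stated to be stratified, so the arms may differ by chance in baseline IOP or lens status, and no adjustment fixed in advance deals with that.

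**Working it through.** **Plan's own figure.** The documents give 120 subjects (60 per arm) without alpha, power, effect size, event rates or margin, so there is no sample-size calculation to reproduce. They also give no correlation between baseline and follow-up IOP and no lens effect. All values of these below are assumptions.

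**Mean IOP, ANCOVA on baseline.** With correlation r between baseline and follow-up IOP, the variance of the arm difference relative to an unadjusted comparison of follow-up means is about 1 - r². The equivalent unadjusted size is 60 / (1 - r²) per arm. Fitting baseline IOP and lens status costs two degrees of freedom, a factor of about (118 - 1) / (118 - 2 - 1) = 117/115 = 1.017. The fourth column applies this factor and treats lens status as uninformative.

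| r (assumed) | 1 - r² | Equivalent n per arm | With cost of two terms |
|---|---|---|---|
| 0 | 1.00 | 60 | 1.02 |
| 0.2 | 0.96 | 62.5 | 0.98 |
| 0.3 | 0.91 | 65.9 | 0.93 |
| 0.4 | 0.84 | 71.4 | 0.85 |
| 0.5 | 0.75 | 80.0 | 0.76 |

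Break-even is where (1 - r²) × 117/115 = 1, so r² = 2/117 and r is about 0.13. In interval width the gain is the square root: √0.91 = 0.95 at r = 0.3 and √0.75 = 0.87 at r = 0.5.

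**Comparing changes from baseline instead.** If the t test were recast as a two-sample test on change, and baseline and follow-up variances were equal, its variance factor would be 2(1 - r): 1.6, 1.4 and 1.0 at r = 0.2, 0.3 and 0.5. At r below 0.5 this is worse than ignoring baseline. ANCOVA relative to change is (1 - r²) / [2(1 - r)] = (1 + r)/2, that is 0.60, 0.65 and 0.75.

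**Binary success.** The check was a simulation of 120 subjects, 2,000 runs per scenario, with no true arm difference. Success was defined as a latent IOP below a cut. The assumed inputs were a 45% pseudophakic share, a normal baseline IOP (not truncated at entry), and a latent correlation, lens effect and site SD as listed. The figures are the variance of the standardized risk difference from logistic regression divided by that of the unadjusted risk difference. Simulation error is a few percent.

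| Success rate | r | Lens effect (SD) | Site SD | Lens only | Lens + baseline IOP |
|---|---|---|---|---|---|
| 80% | 0 | 0 | 0 | 1.01 | 1.02 |
| 80% | 0.2 | 0.2 | 0 | 1.00 | 0.98 |
| 80% | 0.3 | 0.3 | 0.2 | 0.98 | 0.97 |
| 80% | 0.5 | 0.3 | 0.3 | 0.99 | 0.89 |
| 90% | 0 | 0 | 0 | 1.01 | 1.02 |
| 90% | 0.2 | 0.2 | 0 | 1.00 | 0.99 |
| 90% | 0.3 | 0.3 | 0.2 | 1.01 | 1.00 |
| 90% | 0.5 | 0.3 | 0.3 | 1.00 | 0.93 |

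Lens status alone changes almost nothing. Lens status with baseline IOP changes the variance by about +2% to -11%.

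**The case against.** **The unadjusted comparison is valid.** Under randomization, Fisher's test on the success rates needs no covariates, and choosing it is legitimate. That stands: the adjusted success analysis proposed here supports that test and does not replace it.

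**Mean IOP is not a listed endpoint.** Sections 7.1 to 7.4 list success rates, complications, adverse events and IOP spikes. This also stands, and it limits the weight of the larger gain. But section 2.0 makes IOP reduction a purpose of the study, and section 12.0 names a t test that has no evident use other than for quantities such as IOP. If that comparison is made, it should compare the arms.

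**Exploration does not need a named model.** A reader might infer that lens status cannot be explored at all. The text does not support that: Fisher's test and Kaplan-Meier curves can be produced within lens groups, and the wording does not exclude a model. The fair reading is that the method is unspecified.

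**Site.** A reader might also infer that the plan forgoes free power by not stratifying every endpoint by site. The documents do not show this. They say that "7 sites were approved" and that "Each site can enroll a maximum of 30 subjects and a minimum of 5 subjects for each study arm", but give nothing on how much outcomes differ between sites. Seven sites average about 120/7 = 17 subjects, so many strata would have no events for rare complications. In the simulations above, adding six fixed site terms to lens status and baseline IOP moved the variance ratio to between 0.92 and 1.14, a loss in most scenarios. A site-stratified Cochran-Mantel-Haenszel test does have more power than Fisher's test, but so does a plain Pearson test. With an assumed 30% control event rate, log odds ratio -1.2 and site SD of 0 and 0.7, Pearson against stratified power was 0.72 v 0.69 and 0.70 v 0.71 when allocation was not balanced by site, and 0.73 v 0.72 and 0.71 v 0.73 when it was. The difference from Fisher's test is therefore mostly that test's conservatism, which is a separate matter from covariate adjustment.

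**Conclusion.** The point holds as a should-fix matter of method. Section 12.0 names a possible covariate without a method to adjust the arm comparison for it, and its one continuous-data test does not compare the arms. ANCOVA on baseline IOP is a concrete improvement that uses data already collected.

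The size is conditional. For mean IOP the variance falls by 4%, 9% or 25% if r is 0.2, 0.3 or 0.5, before a cost of about 2% for the two terms. The entry rule of IOP above 18 mmHg narrows the baseline range, which argues against counting on the upper end. For the binary primary endpoint the effect is small, about +2% to -11%, and essentially none of it comes from lens status. There is no case for calling this a major loss of power on the safety or primary efficacy comparison, and the gain is not free, because there is a slight loss if baseline IOP is not prognostic. The adjusted estimate also does not settle the claim in section 8.0 that efficacy is as good as trabeculectomy, since no margin is stated.

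**What to change.** Amend section 12.0 as follows.

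1. Compare IOP between arms at each follow-up visit by ANCOVA with arm, baseline IOP and lens status (phakic or pseudophakic), reporting the adjusted difference and 95% CI. Define baseline IOP as one value recorded at screening, since section 9.3.3 calls for two readings an hour apart and section 9.4.2 has its own mean-or-median rule. Keep the paired t test, if at all, as a description of change within each arm.
2. For success at 12 and 24 months (sections 7.1 and 7.2), keep the named unadjusted test. Add a prespecified supporting estimate, the standardized risk difference with 95% CI from logistic regression on arm, baseline IOP and lens status. Standardizing keeps the result on the risk-difference scale, so it can be read beside the unadjusted one. State that the unadjusted difference is reported if the model cannot be fitted: at 90% success there would be only 120 × 0.10 = 12 failures.
3. Keep the unadjusted exact test for rare complications (sections 7.3 and 7.4).
4. Replace the possible-covariate sentence with this fixed list, and label any look at arm effects by lens group as exploratory.

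The cost is a few sentences and one extra model per endpoint, with no new data. The downside is a variance increase of about 2% if neither covariate is prognostic.
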